- Number of incident subjects with infection, osteomyelitis and acute Charcot during the study, will be withdrawn from the study.
- Number of incidences of adverse effects will be reported from all sites and will be withdrawn from the study.
- VR-36 Health Survey, and the Lower Extremity Functional Scale Outcome Questionnaire (self-administered questionnaires) will be used to measure quality of life and provided at beginning of the study and at the study endpoint.
- Rate of transepidermal water loss will be measured weekly subsequent to wound closure and compared in the two groups.

Sample Size Estimation:

From previous studies, we expect that about 20% of the study subjects will heal in the control arm of our study by the 12th week of care. We estimate that the experimental treatment will improve this outcome with 63% of the study subjects healing by the 12th week of care (a healing rate close to that reported in the most recent case series of topical use of timolol on chronic wounds).

We will perform simple allocation of the subjects using an electronic randomization for treatment assignment-since our target enrollment population is fairly homogenous.

The sample size calculation will require the enrollment of 48 subjects (24 subjects in each arm) to provide a power of 80% to detect a difference of 43% (= 63% - 20%) in the rate of ulcer healing between the two arms by using two-sided Fisher's exact test at a significance level of 5%. It is estimated that the overall attrition will be 35%. Specifically, 10% of the subjects who are enrolled will be exited from the study prior to randomization, 10% will not meet the primary endpoint analysis inclusion requirement and 15% will not complete the study due to other factors such as treatment failure, loss to follow-up, adverse events, clinical/safety issues, and/or non-compliance. We will track the various reasons for study exit. Therefore, 138 subjects (69 subjects in each arm) will be recruited into the study after taking into account the overall attrition of 35%.

The consulting statistician will review implementation and compare major baseline demographic and prognostic characteristics to ascertain that randomization was successful. The power analysis was formulated using the STPLAN Version 4.5 (2010) with the input of the study consultant biostatistician.

Analyses:

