The primary outcome is complete ulcer closure by Week 14 (end of the Active Phase) of the study and the rate of ulcer healing by the 12th week of care between the two arms.

[figure not shown]
Hypothesis to be tested: The null hypothesis is that there is no difference in the proportion of subjects with complete wound closure of DFU between the timolol treatment group and the control group. Complete wound closure is defined as 100% closure, or skin re-epithelialization without any drainage present or dressing requirements. Two-sided Fisher's exact test will be used to compare the proportion of complete ulcer closure by Week 12 (end of the Active Phase) of the study and the rate of ulcer healing by the 12th week of care between the two arms. The Kaplan-Meier method will be used to estimate the survival function of time to achieve complete ulcer closure (if less than 12 weeks) for each arm, and a two-sided log-rank test will be used to compare the survival curves between the two arms.

The area of the target ulcer will be summarized by treatment group and visit. Both actual value and change from the previous visits ulcer area will be presented. A second summary of target ulcer area will also be given which will present change from baseline. The weekly change and the percentage weekly change in the target ulcer area from visit to visit will be summarized by treatment group and visit. The two-sided t-test or Wilcoxon rank-sum test as appropriate will be used to compare relative ulcer area from baseline to Week 12 between the two arms.

Chi-square test or Fisher's exact test as appropriate will be used to compare wound healing rates in relationship to wound size, as well as wound healing rates between the treatment groups at the 4-week follow-up and at the 12-week follow-up period and recidivism rate.

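### The planned two-sided Fisher test is valid and meets its stated power, but it is conservative; a precisely defined Boschloo test keeps the 5% limit and gains about 2 to 6 points of power

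*Combined protocol and SAP*

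**What the plan says.** Section 6 (Statistical Design), under Analyses, names a two-sided Fisher test for the primary outcome: "exact test will be used to compare the proportion of complete ulcer closure by Week 12". The Data Analysis part of the Protocol Summary repeats this.

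Under Sample Size Estimation the same test drives the design. The control assumption is "we expect that about 20% of the study subjects will heal in the control arm of our study by the 12th week of care", and the timolol assumption is "63% of the study subjects healing by the 12th week of care", which the plan takes from a case series. The stated requirement is "The sample size calculation will require the enrollment of 48 subjects (24 subjects in each arm"), with the aim "to provide a power of 80% to detect a difference of 43" percentage points, using a "two-sided Fisher's exact test at a significance level of 5" per cent.

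Sections 3 and 6 both specify simple allocation, so an equal split is expected but not forced. The plan does not mention the true error rate of the Fisher test, nor any unconditional exact alternative.

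**The concern.** Fisher's test conditions on the total number of ulcers that close. With few subjects this leaves a coarse set of attainable p-values, and a nominal 5% test can have a true error rate well below 5%. The unused part is power given up without any gain in protection.

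This matters more here than in a large trial. The arms are small and the assumed effect is 43 points. If the true effect is smaller, power falls quickly, and that is where the gain from a less conservative exact test is largest. At 24 per arm, closure in 12 timolol and 5 control subjects gives Fisher p = 0.069, and 11 v 4 gives p = 0.060. Neither is significant under the plan, but both are rejected by Boschloo's test at a guaranteed 5%.

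**Working it through.** **Inputs.** From Section 6, Sample Size Estimation: control 20%, timolol 63%, two-sided 5%, 24 per arm, simple allocation. The 55% and 50% timolol rates below are my assumptions, to show smaller effects.

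**Method.** Let x of n1 control and y of n2 timolol ulcers close. For a rejection region R:

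P(reject) = sum over (x, y) in R of C(n1,x) p1^x (1−p1)^(n1−x) × C(n2,y) p2^y (1−p2)^(n2−y).

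- Power sets p1 = 0.20 and p2 = 0.63 (or 0.55, 0.50).
- Size is the maximum over p1 = p2, on a grid of 1,999 common rates from 0.0005 to 0.9995.
- Fisher: R holds all tables with two-sided Fisher p ≤ 0.05.
- Boschloo: R holds all tables with two-sided Fisher p ≤ c, where c is the largest cut-off that keeps size ≤ 5%. Fisher's size is already below 5%, so c is at least 0.05 and this region contains Fisher's.

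**Step 1: the plan's figure.** Fisher power is 79.5% at 23 per arm and 82.5% at 24. The stated 24 per arm reproduces.

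**Step 2: true size.** At 24/24, Fisher's maximum is 2.94% (at a common rate of 50%) and is 2.60% at a common rate of 20%. Boschloo's maximum is 4.90%. Under simple allocation of 48, the chance of exactly 24/24 is C(48,24)/2^48 = 0.115. At the other splits from 14/34 to 34/14, Fisher's maximum is about 3.2% to 4.2%, and Boschloo's stays at or below 5.0%. All these splits together, 24/24 included, carry 99.8% of the probability.

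**Step 3: power, control rate 20%.** The average weights each split by its binomial probability.

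| Timolol rate | Fisher, averaged | Boschloo, averaged | Fisher, exact 24/24 | Boschloo, exact 24/24 |
|---|---|---|---|---|
| 63% | 84.3% | 86.4% | 82.5% | 87.9% |
| 55% | 66.3% | 70.8% | 63.3% | 72.4% |
| 50% | 52.6% | 58.2% | 49.3% | 59.2% |

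The averaged gains are 2.1, 4.4 (before rounding) and 5.6 points. The 24/24 gains are 5.4, 9.1 and 9.9 points.

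**Step 4: other analysed numbers, 63% v 20%.**

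- Section 6 expects 10% + 15% = 25% loss after randomisation. If that falls on 24 per arm, 24 × 0.75 = 18 remain. At exactly 18/18, power is 68.8% (Fisher) v 75.4% (Boschloo). Averaged over simple allocation of 36, it is 70.9% v 74.2%.
- If 69 per arm are analysed (the recruitment figure of 138), both tests exceed 99.9%.

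**Step 5: which two-sided Boschloo.** SciPy's two-sided version doubles the smaller one-sided p-value. For 4/23 v 0/25 it gives p = 0.062, while Fisher gives p = 0.0455. For 3/18 v 0/30 it gives 0.054 against 0.047. So the containment of Fisher's region does not carry over to that version.

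**The case against.** The strongest reply is that nothing is broken. Design and analysis name the same test, that test controls type I error, and it exceeds the stated 80%. Conservatism is a known property of Fisher's test, and choosing a conditional test over an unconditional one is a legitimate preference. All of that stands.

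Three stronger readings are tempting, and the documents do not support them:

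- A reader might infer that the primary test runs below 3% true error in this trial. That holds only at an exact 24/24 split. The plan specifies simple allocation, under which that split has about an 11% chance.
- A reader might take 5.4 points as the gain at the design effect. That too belongs to 24/24. The average is 2.1 points, and at some near-equal splits almost nothing is gained (26 control and 22 timolol: 85.3% v 85.7%).
- A reader might infer that any test called Boschloo dominates Fisher. Step 5 of the working shows otherwise.

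The 18-per-arm case can also be challenged. Section 6 raises recruitment to 138 for attrition, and Section 3 plans extra recruitment if loss passes 10%, so 24 may already be the number left after losses. The documents do not settle 48 against 138, which is why 18 is shown only as an assumption.

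What survives is the efficiency point. Unlike the uncorrected chi-square test, whose maximum size at 24/24 is 5.95%, the Boschloo test defined here gains power without giving up the 5% guarantee.

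**Conclusion.** The point holds as an inexpensive improvement, not as a flaw. With 48 analysed under simple allocation, the gain is about 2 points at the plan's own effect and about 4 to 6 points if the timolol rate is 55% or 50%. If the arms turn out exactly equal, it is 5.4 points at the plan's effect.

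This rests on about 48 subjects in an unstratified analysis, a 20% control rate, and ordering by the two-sided Fisher p-value. With about 18 per arm the gain is 6.6 points at an equal split and 3.3 on average, but power stays below 80% under either test, so the change does not rescue a shortfall. With 69 per arm there is nothing to gain. The documents do not support calling the Fisher test invalid or the trial underpowered because of it.

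**What to change.** Before unblinding, and provided the primary analysis stays unstratified, amend the Analyses part of Section 6 and its copy in the Protocol Summary along these lines: complete closure will be compared between arms with Boschloo's exact unconditional test at a two-sided 5% level, computed at the realised arm sizes, with tables ordered by the two-sided Fisher p-value and not by doubling a one-sided p-value; Fisher's exact test will be reported as a sensitivity analysis.

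The sample size need not change: 24 per arm already meets 80% under Fisher, and this Boschloo test cannot have less power. The cost is one or two sentences and a short, checked program. The downsides are a less familiar test and the need to state and verify the two-sided definition, because software versions differ.

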PROTOCOL SUMMARY

TITLE OF THE STUDY: MERIT: Beta Adrenergic Antagonist For The Healing of Chronic Diabetic Foot Ulcers

Start Date: 04/01/2017
Ending Date 12/31/2024

PHASE: 2

METHODOLOGY: It is a prospective, randomized, double blinded, controlled, and parallel-group study with 2 arms. Follow up cohort will include a real-world group.

STUDY DURATION: 31 weeks

TREATMENT PHASE: 12 weeks

FOLLOW-UP PHASE: 16 weeks

REAL-WORLD GROUP: 12 weeks

STUDY CENTERS: One centralized study location Multispecialty Wound Healing Clinic at Sacramento VA Medical Center.

Note: Primary Care, Vascular, Podiatry and Dermatology clinics from the at the Veteran Affairs Northern California Health Care System (VANCHS) satellite clinics (Redding, Chico, Martinez, Oakland, McClellan, and Fairfield) will refer patients to the study location.

NUMBER OF SUBJECTS: 2 treatment arms, 24 subjects per arm for a total of 48; Screen-failed patients to be followed passively on the status of their diabetic foot ulcer via CPRS. Additional patients will be screened and enrolled for exploratory follow up to study inflammatory markers in non-healing patients.

STUDY OBJECTIVES: The primary objective of this study is to assess the effectiveness of the topically applied Timoptic-XE® or timolol (a non-selective beta adrenergic receptor antagonist (β BAR)) versus standard of care for the treatment of non-healing diabetic foot ulcers. The primary endpoint will be the measurement of the complete ulcer closure (as defined by “skin re-epithelialization without drainage or dressing requirements) at 12 weeks. The secondary outcomes will be the following: comparison of percent difference change in size from the randomization visit to the endpoint visit (post 12 weeks) between the treatment and control group, the time to wound closure between the two groups, and wound healing rates with impact of wound size between the treatment groups, change in trans-epidermal water loss measurements at sites of healed wounds, measurement of quality of life using Veterans Rand (VR-36) Health Survey, measurement of the Lower Extremity Functional Scale Outcome and the Charlson Comorbidity Index.

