The secondary objective of study is to profile the safety of topically applied Timoptic- XE® in the treatment of DFU. We will monitor serum levels of timolol post-application to determine the plasma concentration of timolol in relation to its systemic bioavailability. Timolol levels will be determined using reversed-phase ultraperformance liquid chromatography and UV detection. The primary safety outcome will be the measurement of timolol serum during the treatment phase.

The secondary safety outcomes will be the following: the mean changes from baseline in systolic and diastolic blood pressure in mmHg, the mean changes from baseline in heart rate in beats per minute, and the measurement of all the adverse events associated with the use of Timoptic-XE®.

INCLUSION CRITERIA:

1. Male or female subject of any race 18 years old or older
2. Lower extremity ulcer located anywhere on the foot up to the ankle:
 - a. Of more than 30 days duration and less than 2 years duration (medically documented)
 - b. Surface area between 0.5cm² and 20cm² (as measured with the Silhouette imaging system at randomization). The ulcer with largest surface area meeting inclusion criteria will be selected as index ulcer
 - c. If two ulcers present with the same surface area, the ulcer of the longest duration will be selected as index ulcer
3. Documented Ankle Brachial Index (ABI) between 0.8 and 1.2 on the study limb or toe pressure over 65mmHg within 3 months of screening phase
4. Documented biopsy report to rule out malignancy of ulcer of > 6 months duration

EXCLUSION CRITERIA*:

A subject will be excluded from the study if any of the following criteria are met:

1. Ulcer of non-diabetic etiology, such as venous, arterial and burn wounds
2. Index ulcer is less than 3 cm in distance from any other ulcer on the same extremity
3. There are greater than 3 ulcers on the study foot
4. Index ulcer presents with any of the following: cellulitis, osteomyelitis, exposed bone, tendon or fascia, purulent exudate or gangrene
5. Index ulcer shows evidence of infection (defined as a moderate or severe rating of all of the following clinical signs/symptoms: 1) increased warmth, 2) increased pain, 3) erythema, and 4) malodorous exudate at Screening or at Randomization (Visit 1), OR total organism count > 1 x 10⁵ colony forming units (CFU) from the screening visit study ulcer culture sample)

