Hypothesis to be tested: The null hypothesis is that there is no difference in the proportion of subjects with complete wound closure of DFU between the timolol treatment group and the control group. Complete wound closure is defined as 100% closure, or skin re-epithelialization without any drainage present or dressing requirements. Two-sided Fisher's exact test will be used to compare the proportion of complete ulcer closure by Week 12 (end of the Active Phase) of the study and the rate of ulcer healing by the 12th week of care between the two arms. The Kaplan-Meier method will be used to estimate the survival function of time to achieve complete ulcer closure (if less than 12 weeks) for each arm, and a two-sided log-rank test will be used to compare the survival curves between the two arms.

The area of the target ulcer will be summarized by treatment group and visit. Both actual value and change from the previous visits ulcer area will be presented. A second summary of target ulcer area will also be given which will present change from baseline. The weekly change and the percentage weekly change in the target ulcer area from visit to visit will be summarized by treatment group and visit. The two-sided t-test or Wilcoxon rank-sum test as appropriate will be used to compare relative ulcer area from baseline to Week 12 between the two arms.

Chi-square test or Fisher's exact test as appropriate will be used to compare wound healing rates in relationship to wound size, as well as wound healing rates between the treatment groups at the 4-week follow-up and at the 12-week follow-up period and recidivism rate.

Additional secondary analyses to evaluate the association of specific wound characteristics (such as wound size, wound location) and subject characteristics (body mass index, chronicity of the wound, history of DVT, length of diabetes, HbA1c, and ABI/toe pressure will be conducted using logistic regression. Further logistic regression will be used to investigate the relationship between the occurrence of each type of adverse event and treatment in order to adjust for each of the potential confounding factors previously listed.

A two-way ANOVA with a post hoc test will be used to determine the relationship between timolol serum levels and wound healing.

Further statistical analysis will be used to determine the relationship between serum inflammatory markers and wound healing.

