6. STATISTICAL DESIGN

Measures:

Measures will be collected at baseline, weekly thereafter, with primary endpoint of complete healing at Visit 14/Week 14, and final secondary endpoint measurement at Visit 17/Week 31. The ulcer will be assessed weekly and will be treated as described above. A designated inter-observer (blinded to the treatment of the subjects) will regularly review images and physical exam findings to determine primary and secondary endpoints. The following measurements will be taken: size (surface area calculation), photos (digital includes ruler) and complete foot ulcer assessment (description of ulcer/characteristics), before and after debridement. Subjects where ulceration healed earlier than Visit 14/Week 14 will have follow-up assessment one week after healing, a 2nd assessment a week after, then 4 monthly visits at Weeks 19, 23, 27 & 31. If the ulceration healed after 12 weeks, then the subjects will be similarly assessed. The subject with healed ulcer will also return for follow-up visits Weeks 19, 23, 27 & 31 (visits 16, 17, 18 and 19).

During the study, if ulceration appears to be infected as determined by clinical presentation characterized by the presence of two or more signs of inflammation, the clinician will follow the protocol of obtaining wound culture for microbiology, radiographs, blood work (CBC, chemistry panel, sedimentation rate, and C-reactive protein), and treatment immediately with appropriate antibiotics. Subjects with infected ulcers will be withdrawn from study and investigators will be notified. In addition, adverse events will be well documented and treated per protocol, and subjects will be withdrawn from study.

Clinical Outcomes:

- The percentage of subjects that have complete closure of ulceration by Visit 14/Week 14 and Visit 17/Week 31. Complete healing will be defined as full re-epithelialization with no drainage, or callus formation and remains closed after 1 week of wound closure.

- Rate of wound healing to achieve complete closure. Weekly measurements of surface area will be recorded using Silhouette Mobile™ ulcer tracing and surface area calculation.
- A diabetic foot ulcer assessment form will be filled out at weekly follow-up visits, that describes characteristics of ulceration including peri-ulcer erythema, wound margins, fibrin, granular tissue, peri-ulcer pruritus, edema and location, pain, amount of drainage and type, amount of epithelialization, pain level, depth, and bioburden.

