Additional secondary analyses to evaluate the association of specific wound characteristics (such as wound size, wound location) and subject characteristics (body mass index, chronicity of the wound, history of DVT, length of diabetes, HbA1c, and ABI/toe pressure will be conducted using logistic regression. Further logistic regression will be used to investigate the relationship between the occurrence of each type of adverse event and treatment in order to adjust for each of the potential confounding factors previously listed. A two-way ANOVA with a post hoc test will be used to determine the relationship between timolol serum levels and wound healing. For demographic and clinical characteristic data at baseline, continuous variables will be summarized (when appropriate) by using mean, median, standard deviation, co-efficient of variation, minimum value and maximum value. Categorical variables will be summarized with frequency tables. Baseline comparability between the two treatment groups will be assessed by using the independent two-sample t-test or Wilcoxon rank-sum test and the Chi-square test or Fisher's exact test. Finally, we will use ANCOVA to analyze the quality of life (QOL) using the VR-36 Health Survey and the Lower Extremity Functional Scale Outcome Questionnaire, and the Charlson Comorbidity Index.

Timeline and Milestones:

7. APPENDIX 1 – Wound Scoring System

Ulcer Characteristic Form

Size: Dimensions _____ x _____ x _____ cm

Number of leg ulcers: Right Leg _____ Left Leg _____

If multiple ulcers, write distance from the study ulcer to other ulcers: _____ cm

Where is the study ulcer located? Right Leg Left Leg

Describe the study ulcer location: foot ankle low calf high calf other:

Describe the study ulcer position: dorsal ventral medial anterior lateral
 posterior

How old is the current target diabetic foot ulcer (in weeks): _____ weeks

Event that precipitated target ulcer: Ill-fitting shoes Poor foot care Acute accidental event (trauma) Not determined Other, please specify: _____

Has the study ulcer ever healed and recurred? Yes No

Has the subject ever suffered a DVT in the study limb? Yes No

Does the Study Limb/Leg Ulcer present with any of the following? (Check all that apply)

Hyperpigmentation Varicosities Dermatitis Swelling/Edema
 Lipodermatosclerosis Other: _____

	Parameter	Assessment	Score	Total
1	Erythema	Absent	0	
		Mild	1	
		Moderate	2	
		Severe	3	
2	Induration	Absent	0	
		Mild	1	
		Moderate	2	
		Severe	3	

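### The secondary outcome on wound size and treatment group has no specified analysis that estimates whether the timolol effect varies with ulcer size

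*Combined protocol and SAP*

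**What the plan says.** **The outcome.** The Protocol Summary (Study Objectives) and section 2 both include, among the secondary outcomes, "wound healing rates with impact of wound size between the treatment groups".

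**The named test.** Under Data Analysis in the Summary and under Analyses in section 6, a chi-square or Fisher's exact test, as appropriate, "will be used to compare wound healing rates in relationship to wound size". The same sentence applies these tests to "wound healing rates between the treatment groups at the 4-week follow-up and at the 12-week follow-up period", and to recidivism. No size classes are given for the first comparison.

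**The second analysis naming size.** The next paragraph begins "Additional secondary analyses to evaluate the association of specific wound characteristics (such as wound size, wound location", adds subject characteristics, and ends "will be conducted using logistic regression". It does not state the response, the coding of size, whether treatment is in the model, or any treatment-by-size term.

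**The measurement.** Area is continuous: "Weekly measurements of surface area will be recorded using Silhouette Mobile" (section 6, Clinical Outcomes). Eligibility allows "Surface area between 0.5cm² and 20cm²" at randomisation.

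**The concern.** The natural reading of the outcome is a question about two factors together: how size bears on healing under timolol compared with control. The sentence on tests gives two comparisons, one of healing by size and one of healing by arm. Neither joins the two factors.

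A significant healing-by-size table could arise because large ulcers heal less often in both arms, because size matters in one arm only, or because size happened to be unbalanced between arms. The table cannot separate these. The undefined classes are a further gap: the dispensing table in section 4.2 and the wound score in Appendix 1 use different size bands, neither is tied to this test, and cut-points could be chosen after the data are seen.

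At stake is one secondary outcome. The primary Fisher comparison does not depend on it.

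**Working it through.** **1. The plan's own figure.** The inputs are in section 6, Sample Size Estimation: "we expect that about 20% of the study subjects will heal in the control arm", 63% with timolol, two-sided Fisher's exact test at 5%, 80% power. Power is the sum, over all pairs (a, b) of healed counts with Fisher p ≤ 0.05, of Bin(a; n, 0.20) × Bin(b; n, 0.63). Full enumeration gives 79.5% at n = 23 and 82.5% at n = 24 per arm. The stated 24 per arm (48 in total) reproduces and is not in dispute. The documents give no figure for the size analysis.

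**2. What the two planned tables can see.** Take 24 per arm, split 12 small and 12 large, with 15/24 (62.5%) healed on timolol and 5/24 (20.8%) on control. Two constructed trials:

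| Healed | Timolol small | Timolol large | Control small | Control large |
|---|---|---|---|---|
| Trial A | 9/12 | 6/12 | 1/12 | 4/12 |
| Trial B | 6/12 | 9/12 | 4/12 | 1/12 |

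In both, healing by size is 10/24 v 10/24 (Fisher p = 1) and healing by arm is 15/24 v 5/24. In A, the treatment odds ratio is (9 × 11)/(3 × 1) = 33 in small ulcers and (6 × 8)/(6 × 4) = 2 in large ones. In B, these are exchanged. The two pooled tables are identical, yet the dependence on size is opposite.

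**3. Simulation at 24 per arm.** The model is logit P(closure) = intercept(arm) + slope(arm) × log2(area). Area is assumed log-uniform on 0.5 to 20 cm², which is log2(40) = 5.32 doublings. Healing rates below are set at the 25th and 75th percentiles, 0.5 × 40^0.25 = 1.3 cm² and 0.5 × 40^0.75 = 8.0 cm². They are assumptions, because the documents give no healing rates by size. There were 2,000 trials per row, so the simulation error is at most √(0.25/2000) = 1.1 points.

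| Setting | Control, small/large | Timolol, small/large | Pooled median-split Fisher, healing by size | Interaction, likelihood-ratio test |
|---|---|---|---|---|
| No size effect | 20/20% | 63/63% | 3.1% | 7.0% |
| Same size effect in both arms | 30/13% | 74/50% | 21.8% | 7.6% |
| Timolol arm only | 20/20% | 80/46% | 15.2% | 27.0% |
| Timolol arm only, steeper | 20/20% | 90/36% | 29.6% | 55.4% |
| Opposite directions | 10/30% | 73/53% | 3.5% | 46.8% |
| Opposite directions, steeper | 5/35% | 83/43% | 2.8% | 89.0% |

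The pooled table rejects in about 22% of trials when the odds ratio for treatment does not vary with size, and in about 3% when it varies strongly in opposite directions. A separate set of runs with slopes of 0.5 per doubling in opposite directions gave 7% for a median-split chi-square, about its null rate of 6.7%, and 62% for the interaction.

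**4. What grouping costs.** With the same slope in both arms, 1,500 trials per setting gave these rates of detecting the size association:

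| Slope per doubling | Median-split chi-square | Continuous, unadjusted | Continuous, adjusted for treatment |
|---|---|---|---|
| 0.35 | 26% | 31% | 38% |
| 0.50 | 40% | 51% | 60% |

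Of the 12-point gap at 0.35, 31 − 26 = 5 points come from keeping area continuous; of the 20-point gap at 0.50, 51 − 40 = 11 points do. The rest comes from adjusting for treatment.

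**5. What an interaction can deliver with 48 subjects.** If area matters only in the timolol arm at 0.5 log-odds per doubling, the ordinary likelihood-ratio test has about 22% power (21% to 24% across runs), with a false-positive rate near 7%. A penalised fit gave 4.6% false positives and about 17% power. As a rough guide to precision, 22% power under a normal approximation implies a standard error of about 0.5/(1.96 − 0.77) = 0.42, so a 95% half-width of 1.96 × 0.42 = 0.82, a factor of exp(0.82) = 2.3 either way. An estimated ratio of odds ratios of exp(−0.5) = 0.61 per doubling would then run from about 0.27 to 1.4. This is optimistic, because the ordinary test rejects too often.

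**The case against.** The strongest reply is that the chi-square/Fisher sentence is only half of the plan for wound size. A reader of that sentence alone might infer that the plan as a whole discards the continuous measurement. The documents do not support this: the planned logistic regression names wound size and could take area as it is measured. This stands. What remains is that the model's response, coding and treatment-by-size term are unstated.

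Second, the text does not say that the size table is pooled over arms or cut at the median; both are assumptions of the calculation. Comparing arms within size strata would fit the wording. This also stands, but strata would still need classes, and separate p-values by stratum do not estimate the difference in effect.

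Third, the outcome is loosely worded. It may mean healing between arms allowing for size, and the Efficacy Endpoints list in the Protocol Summary gives only a rate of ulcer healing, with no size component. So a reader might infer that the trial cannot answer one of its secondary questions, but that goes further than the documents allow. The data will exist; the analysis is unspecified under the more natural of two readings.

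Fourth, a reader might put the whole of the power gaps in step 4 down to grouping. About half or less is closer at the smaller slope (5 of 12 points), and just over half at the larger (11 of 20).

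Fifth, in the timolol-only setting a penalised interaction test (about 17%) has no more power than the pooled chi-square (17% to 19%). That is correct. The gain there is that the estimate addresses the listed outcome.

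**Conclusion.** The point holds as a minor gap in specification. The named test requires undefined size classes, and a healing-by-size table does not estimate whether the timolol effect varies with ulcer size. No section states a treatment-by-size term, including in the logistic regression that could carry it. The constructed example in step 2 shows this without any assumed slope. The simulated sizes rest on 24 per arm, on the plan's 20% and 63% as overall or mid-range closure rates, on log-uniform area, and on assumed slopes; they show what the methods can detect and do not predict this trial.

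A reader might also infer from the dispensing table that the effect should fade as area rises. The documents give no effect by size, and drops per cm² in that table do not fall steadily: about 1/1.9 = 0.53 at 1.9 cm², but 2/2.9 = 0.69 at 2.9 cm². The point does not rest on that argument. The sample size and the primary test are untouched.

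**What to change.** For this outcome, use the logistic model already planned in place of the chi-square/Fisher test, and complete its specification:

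- **Response:** complete closure at the primary time point, as fixed for the primary analysis.
- **Terms:** treatment, log2(baseline area) as a continuous variable, and treatment × log2(baseline area), with area taken at randomisation.
- **Fit:** penalised likelihood, because the ordinary likelihood-ratio test over-rejects at this sample size.
- **Report:** the odds ratio per doubling of area in each arm, and the interaction, each with a 95% interval and labelled exploratory.

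Keep the chi-square/Fisher tests for the plain comparisons between arms at 4 and 12 weeks.

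The cost is SAP wording: no new data, no added subjects and no change to the primary test. The downside is a wide interaction interval at 48 subjects, so its value lies in the estimate and interval and not in a significance test.
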